### 2.1.2. Immunogenicity Visit Windows

For immunogenicity summaries and tabulations per time point, assessments will be allocated to an analysis visit based on the planned visit as captured in the CRF. Visits that are out of the protocol-defined visit windows (see table below) will not be included in the immunogenicity summaries and tabulations per timepoint. However, they may be included in sensitivity analyses.

Analysis timepoint	Subset	Reference day	Target day (counted from the reference day)	Window
Baseline	Immuno Subset / All Revaccination Subcohorts	Day of vaccination 1	1	(-inf, 1]
Day 15	Immuno Subset / All Revaccination Subcohorts	Day of vaccination 1	15	[15, 18]
Day 85	Immuno Subset	Day of vaccination 1	85	[78, 92]
Day 169	Immuno Subset	Day of vaccination 1	169	[155, 183]
Day 365	Immuno Subset / Revaccination Subcohort 1B, 2B, 1C, 2C, 1D and 2D	Day of vaccination 1	365	[304, 426]
Day 365	Revaccination Subcohorts 1A, 2A	Day of vaccination 2	1	[1]
Day 379	Revaccination Subcohorts 1A, 2A	Day of vaccination 2	15	[15, 18]
Day 393	Revaccination Subcohorts 1A, 2A	Day of vaccination 2	29	[29, 32]
Day 449	Revaccination Subcohorts 1A, 2A	Day of vaccination 2	85	[78, 92]
Day 533	Immuno Subset	Day of vaccination 1	533	[519, 547]
Day 533	Revaccination Subcohorts 1A, 2A	Day of vaccination 2	169	[155, 183]
Day 730	Immuno Subset	Day of vaccination 1	730	[669, 791]
Day 730	Revaccination Subcohort 1A	Day of vaccination 2	365	[334,396]
Day 730	Revaccination Subcohort 1B, 2B	Day of vaccination 2	1	[1]
Day 730	Revaccination Subcohort 2A	Day of vaccination 3	1	[1]
Day 737	Revaccination Subcohort 1B, 2B	Day of vaccination 2	8	[6, 10]
Day 737	Revaccination Subcohort 2A	Day of vaccination 3	8	[6, 10]
Day 744	Revaccination Subcohort 1B, 2B	Day of vaccination 2	15	[15, 18]
Day 744	Revaccination Subcohort 2A	Day of vaccination 3	15	[15, 18]
Day 758	Revaccination	Day of vaccination 2	29	[29, 32]

Analysis timepoint	Subset	Reference day	Target day (counted from the reference day)	Window
	Subcohort 1B, 2B			
Day 758	Revaccination Subcohort 2A	Day of vaccination 3	29	[29, 32]
Day 814	Revaccination Subcohort 1B, 2B	Day of vaccination 2	85	[78, 92]
Day 814	Revaccination Subcohort 2A	Day of vaccination 3	85	[78, 92]
Day 898	Revaccination Subcohort 1B, 2B	Day of vaccination 2	169	[155, 183]
Day 898	Revaccination Subcohort 2A	Day of vaccination 3	169	[155, 183]
Day 912	Immuno Subset	Day of vaccination 1	912	[898, 926]
Day 1095	Revaccination Subcohort 1C and 2C	Day of vaccination 2	1	[1]
Day 1095	Revaccination Subcohort 1B	Day of vaccination 2	365	[334,396]
Day 1095	Revaccination Subcohort 2B	Day of vaccination 3	1	[1]
Day 1095	Revaccination Subcohort 2A	Day of vaccination 3	365	[334,396]
Day 1102	Revaccination Subcohort 2B	Day of vaccination 3	8	[6, 10]
Day 1109	Revaccination Subcohort 1C and 2C	Day of vaccination 2	15	[15, 18]
Day 1109	Revaccination Subcohort 2B	Day of vaccination 3	15	[15, 18]
Day 1123	Revaccination Subcohort 2B	Day of vaccination 3	29	[29, 32]
Day 1179	Revaccination Subcohort 1C and 2C	Day of vaccination 2	85	[78, 92]
Day 1179	Revaccination Subcohort 2B	Day of vaccination 3	85	[78, 92]
Day 1263	Revaccination Subcohort 1C and 2C	Day of vaccination 2	169	[155, 183]
Day 1263	Revaccination Subcohort 2B	Day of vaccination 3	169	[155, 183]
Day 1460	Revaccination Subcohort 1D and	Day of vaccination 2	1	[1]

Analysis timepoint	Subset	Reference day	Target day (counted from the reference day)	Window
	2D			
Day 1460	Revaccination Subcohort 1C and 2C	Day of vaccination 2	365	[334,396]
Day 1460	Revaccination Subcohort 2B	Day of vaccination 3	365	[334,396]
Day 1474	Revaccination Subcohort 1D and 2D	Day of vaccination 2	15	[15, 18]
Day 1544	Revaccination Subcohort 1D and 2D	Day of vaccination 2	85	[78, 92]
Day 1628	Revaccination Subcohort 1D and 2D	Day of vaccination 2	169	[155, 183]

Immunogenicity samples that are not contained in these windows will not be included in the analysis. However, they may be included in sensitivity analyses.

Immunogenicity samples taken during an ARI will be allocated to an analysis timepoint based on the relative day during the ARI and the below windowing. The relative day during the ARI is determined as ARI visit date – ARI onset date +1.

Analysis timepoint	Reference day	Target day (counted from the reference day)	Window
ARI Day 3-5	Onset day of ARI	4	[1,7]
ARI Day 29	Onset day of ARI	29	[22,36]

Immunogenicity samples that are not contained in these windows will not be included in the analysis of ARI samples. However, they may be included in sensitivity analyses.

## 2.2. Pooling Algorithm for Analysis Centers

Site was not part of the randomization algorithm. Data from all study sites will be pooled together.

## 2.3. Analysis Sets

Vaccination assignment will follow the as treated principle.

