### **2.3.1. Full Analysis Set (FAS)**

The Full Analysis Set (FAS) will include all randomized participants with a documented vaccine administration, regardless of the occurrence of protocol deviations. The FAS is the primary safety population. The analysis of solicited and unsolicited AEs after the Day 1 vaccination will be restricted to a subset of the FAS (i.e., the Safety Subset). The analysis of solicited and unsolicited AEs after revaccination on Day 365 (Month 12)/Day 730 (Month 24)/Day 1095 (Month 36)/Day 1460 (Month 48) will be restricted to participants of the Revaccination Subcohorts that are part of the FAS.

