### **2.3.3. Per Protocol Efficacy Population (PPE)**

The Per-protocol Efficacy (PPE) population will include all randomized and vaccinated participants excluding participants with major protocol deviations expecting to impact the efficacy outcomes. The list of major protocol deviations to be excluded from the efficacy analysis will be specified in the major protocol deviations criteria document which will be finalized before database lock and unblinding. Any participant with an RT-PCR-confirmed RSV-mediated ARI with onset within 14 days after vaccination will be excluded from the PPE population. Participants who discontinue within 14 days after vaccination will be excluded from the PPE population as well.

The PPE population is the primary efficacy population. Sensitivity efficacy analyses will also be performed on the FAS.

For exploratory efficacy analyses focusing on data from the second RSV season only, the participants of Revaccination Subcohort A will additionally be excluded. For analyses focusing on data from the third RSV season, participants of Revaccination Subcohorts A and B will be excluded. For exploratory analyses focusing on data over season two and three and over all three RSV seasons, second and third RSV season data will be excluded for the participants of Revaccination Subcohort A, and third RSV season data will be excluded for participants of Revaccination Subcohort B. Participants who develop major MPDs expecting to impact the efficacy outcomes and occurring up to the considered season will be **additionally** excluded from the PPE when focusing on data including the second or third RSV season. For exploratory analyses focusing on data over season two and three and over all three RSV seasons, only the data of the season in which the major MPDs expecting to impact the efficacy outcomes occur and the data of the seasons thereafter will be excluded. Note that in case an ARI started in RSV Season 1 or 2 and continues during Season 2 or 3 respectively, all ARI information will be considered part of the first or second year analysis, regardless if they were collected during the second or third year.

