#### 4.4.2.2. Analysis Methods

For each of the 3 primary endpoints the following will be performed: an exact Poisson regression will be fitted with the event rate, defined as the number of cases over the follow-up time (offset) as dependent variable and the vaccination group and age and being at increased risk for severe RSV disease (both as stratified) as independent variables. For cases, the follow-up time is defined as the time between vaccination and the occurrence of the first event (according to the considered endpoint), for non-cases, it is the time between vaccination and the end of season visit. In case the EOS visit is missing then the 15th of May 2020 will be used. However, for participants that discontinued before the end of the season and had an event (according to the considered endpoint), the follow-up time is defined as the time between vaccination and the occurrence of the first event and for participants that discontinued before having an event, follow-up time is the time between vaccination and the date of last contact (date of discontinuation).

Note: in case more than one end of season visits are available, the latest will be used to determine the follow up time.

Thus, all participants are included in the analysis according to their follow-up time. The exact one sided p-value corresponding to vaccination group will be compared with the one sided cut-off as described above (Section 4.4.1.1).

If the p-value is below the cut-off for at least 1 of the 3 primary endpoints, proof of concept is demonstrated. The individual exact 2-sided CIs ( $1-2 \times$  cut-off) for the VE (1-relative risk rate), measured by each of the 3 endpoints, will be calculated from the regression model described above and graphically depicted with forest plots.

The primary analysis will be performed on the PPE population, which will take cases into account with an onset at least 14 days after vaccination.

As sensitivity analyses the above Poisson model will be repeated similar to the primary analysis:

- based on the FAS (which also does not take into account the restriction on the onset [at least 14 days] and will count cases from vaccination on Day 1 onwards). RT-PCR results from samples that were out of stability, but tested RSV positive are taken into account in this analysis.
- based on the PPE set but taking into account only RT-PCR test results from the central laboratory (i.e., excluding the local test results for hospitalized participants)

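### The as-treated rule in SAP 2.3 covers the FAS efficacy sensitivity analyses too, so no planned efficacy analysis groups participants as randomised

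*SAP*

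**What the plan says.** Section 2.3 sets the assignment rule in one sentence, before any set is defined: "Vaccination assignment will follow the as treated principle". It makes no exception by set or by endpoint.

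The sets follow. Section 2.3.1: "The Full Analysis Set (FAS) will include all randomized participants with a documented vaccine administration, regardless of the occurrence of protocol deviations". The same section gives the set its main role: "The FAS is the primary safety population". Section 2.3.3 then gives it a second one: "The PPE population is the primary efficacy population. Sensitivity efficacy analyses will also be performed on the FAS".

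Section 4.4.2.2 lists the FAS analysis first among the season-one sensitivity analyses: "based on the FAS (which also does not take into account the restriction on the onset". It also lets out-of-stability samples that tested RSV positive count. The same section adds an unstratified exact binomial test on the PPE and the FAS. Section 5.4.1.2 repeats the FAS analysis for the later seasons, with extra rules on revaccination subcohorts and earlier discontinuations.

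**The concern.** As-treated grouping is normal for safety and acceptable for a per-protocol set. It is unusual for an efficacy analysis on the set that keeps participants whatever their protocol deviations. The PPE removes people for events after randomisation: major deviations, RSV illness within 14 days of vaccination, and discontinuation within 14 days. The FAS is the only set in the plan on which efficacy is analysed without those removals.

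For a participant given the wrong product, the two ways of grouping disagree. Under Section 2.3 that person and any event move to the arm of the product received. If an administration error is related to site, timing or participant characteristics, the move can bias the comparison, and the plan has no efficacy analysis that would show it.

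**Working it through.** **1. Does any section restore the randomised group?**

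| SAP section | What it changes for FAS efficacy | Group assignment changed? |
|---|---|---|
| 2.3.1 | Set membership: randomised and vaccinated | No |
| 2.3.3 | Gives the FAS a sensitivity role | No |
| 4.4.2.2, Poisson model on FAS | 14-day onset rule; out-of-stability positives | No |
| 4.4.2.2, exact binomial on FAS | Drops the strata | No |
| 5.4.1.2, FAS, later seasons | Onset rule, stability rule, subcohort and discontinuation rules | No |

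The phrase 'as stratified' in 4.4.2.2 qualifies the age and risk covariates, not the vaccination group. ITT is in the abbreviation list, but Section 2.3 defines no such set. The as-treated rule therefore governs every efficacy analysis.

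**2. Expected size.** The SAP does not say how many participants received the wrong product, so I assume x per arm, with x from 0 to 58 (0% to 2% of the 2,900 per group in Table 1). The rates are the planning values in Section 4.4.1.1.1: 0.75% incidence, taken as the placebo rate, and 70% VE, giving 0.225% on vaccine.

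- Vaccine arm as randomised: [(2,900 − x) × 0.00225 + x × 0.0075] events
- Placebo arm as randomised: [(2,900 − x) × 0.0075 + x × 0.00225] events
- VE as randomised = 1 − ratio of the two
- Expected events that change arm = x × (0.0075 + 0.00225)

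| x per arm | Expected events, vaccine v placebo | VE as randomised (as treated 70%) | Expected events moved |
|---|---|---|---|
| 0 | 6.53 v 21.75 | 70.0% | 0 |
| 5 | 6.55 v 21.72 | 69.8% | 0.05 |
| 29 | 6.68 v 21.60 | 69.1% | 0.28 |
| 58 | 6.83 v 21.45 | 68.2% | 0.57 |

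**3. Can one case matter?** Section 4.4.1.1 applies the corrected alpha to sensitivity analyses, and 4.4.2.2 compares a one-sided p-value with it. I first reproduced the SAP's own cut-offs, using a one-sided equal-boundary calculation with correlation √(IFi/IFj).

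| Input | Recomputed | SAP |
|---|---|---|
| IF (0.7, 1), alpha 0.05 | 0.0335 | 0.0335 |
| IF (0.36, 1), alpha 0.05 | 0.02874 | 0.02874 |
| IF (0.56, 0.72, 1), alpha 0.0335 | 0.0174 | 0.0175 |

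With no interim analysis, the full 0.05 is split over the three endpoints. Using the SAP's example fractions (0.56, 0.72, 1), the cut-off is 0.0268.

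Take 18 events, the Case Definition 2 count at which the primary analysis goes ahead without an interim (Table 4). That threshold is counted on the PPE, so its use for the FAS is illustrative. With 1:1 allocation and an unstratified conditional binomial:

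- 5 v 13 as randomised: P(Bin(18, 0.5) ≤ 5) = 0.0481, above 0.0268
- 4 v 14 after one vaccine-arm case moves to placebo: P(Bin(18, 0.5) ≤ 4) = 0.0154, below 0.0268

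**4. How likely is that flip?** It needs a participant randomised to vaccine, given placebo, who becomes a case. With 5 such participants the chance is 1 − (1 − 0.0075)^5 = 3.7%. It also needs a 5 v 13 split. At 70% VE a case falls in the vaccine arm with probability 0.3/1.3 = 0.231, and P(Bin(18, 0.231) = 5) = 18.5%. Multiplied as if independent, these give about 0.7%. With one such participant it is 0.0075 × 0.185 = 0.14%.

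**The case against.** The strongest reply is that this is an explicit, prespecified choice and contradicts nothing. The SAP never promises an intention-to-treat analysis. It calls the FAS the primary safety set and says what the FAS efficacy analysis varies: the onset rule and the sample-stability rule. That stands. A reader might infer that the FAS analysis was declared as a test free of post-randomisation choices and fails its stated aim, but the SAP states no such aim.

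Second, nothing in the document suggests that anyone received the wrong product, and the one-case flip is a chosen boundary case, with probability below 1% under the assumptions above. That stands too. The flip shows how sensitive the analysis is, not what to expect.

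Third, proof of concept is tested on the PPE (Sections 1.3 and 4.4.2.2). A reader might infer that the as-treated rule puts the trial's main conclusion in doubt. It does not, because crossing a cut-off in the FAS changes no decision.

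Fourth, changing the label alone does not give a full randomised comparison. The FAS leaves out randomised participants who were never vaccinated. In the later seasons Section 5.4.1.2 also drops revaccination subcohorts and earlier discontinuations. This is correct and limits what the fix can claim.

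Fifth, the season-one primary analysis has been run; Section 1.6 refers to it in the past tense. A change to 4.4.2.2 now would follow unblinding, so it cannot be presented as prespecified.

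None of these replies identifies a planned efficacy analysis by randomised group.

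**Conclusion.** The point holds on the text: one unqualified rule covers every set, and no efficacy section departs from it. The FAS sensitivity analyses would move any wrong-product participant to the other arm.

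The effect is zero if nobody was mis-dosed. At an assumed 0% to 2% per arm and the SAP's planning rates, as-randomised VE is 0 to 1.8 percentage points below an as-treated 70%, with fewer than 0.6 events expected to move. A single case can still carry the season-one FAS result across its cut-off at about 18 events, but this is unlikely. The result assumes equal numbers mis-dosed in each arm, risk that follows the product received, and errors unrelated to risk; errors related to risk could have a larger effect.

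This is a worthwhile and inexpensive correction to supportive analyses. It does not bear on the PPE-based decision, and it is not evidence that any error occurred. The protocol is not at hand and may say more, but Section 2.3 states the rule itself and does not defer to the protocol.

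**What to change.** Add to Section 2.3 that efficacy analyses on the FAS (Sections 4.4.2.2 and 5.4.1.2) group participants by randomised assignment, while safety, PPI and PPE remain as treated.

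- **End-of-efficacy analyses:** apply the sentence prospectively.
- **Season one:** report the number of participants given the wrong product, by arm. If it is zero, say so and stop. If not, add an as-randomised rerun of the FAS efficacy analysis, labelled post hoc.
- **Wording:** call the result an as-randomised comparison among vaccinated participants. It is not full ITT and does not undo the later-season subcohort and discontinuation exclusions.

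The cost is one SAP sentence, one grouping variable in the FAS efficacy programs, a late amendment to document and, if mis-dosing occurred, one extra labelled analysis.

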### **2.3.1. Full Analysis Set (FAS)**

The Full Analysis Set (FAS) will include all randomized participants with a documented vaccine administration, regardless of the occurrence of protocol deviations. The FAS is the primary safety population. The analysis of solicited and unsolicited AEs after the Day 1 vaccination will be restricted to a subset of the FAS (i.e., the Safety Subset). The analysis of solicited and unsolicited AEs after revaccination on Day 365 (Month 12)/Day 730 (Month 24)/Day 1095 (Month 36)/Day 1460 (Month 48) will be restricted to participants of the Revaccination Subcohorts that are part of the FAS.

### **2.3.2. Per Protocol Immunogenicity Population (PPI)**

The Per-protocol Immunogenicity (PPI) population will include all randomized and vaccinated participants, for whom immunogenicity data are available. Samples taken after a participant experienced a major protocol deviation (MPD) expected to impact the immunogenicity outcomes (based on the DV.DVSTDC), will be excluded from the PPI. The list of major protocol deviations to be excluded from the immunogenicity analysis will be documented in the major protocol deviations criteria document that will be finalized prior to database lock. These will also be indicated in the locked database. The analysis of immunogenicity will focus on 5 subsets of the PPI, i.e. the Immuno Subset and the 4 Revaccination Subcohorts.

In addition, for participants who experience a natural RSV infection (based on RT-PCR, or other sources), samples taken after the natural infection will not be taken into account in the assessment of the immunogenicity.

Moreover, immunogenicity samples taken outside of the prespecified visit windows (see Section 2.1.2) will be excluded from the immunogenicity analysis.

The PPI population is the primary immunogenicity population. For key tables, sensitivity immunogenicity analyses will also be performed on the FAS, including participants that are part of the Immuno Subset or the Revaccination Subcohorts for whom immunogenicity measures are available. Excluded samples (samples taken after the natural RSV infection or after major protocol deviations impacting immunogenicity and samples taken outside of the window) will be taken into account as well in the sensitivity analysis.

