### **4.3. Immunogenicity Analysis**

The analysis of immunogenicity will use the PPI set, focusing on the immunogenicity subset.

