**Immunogenicity against natural infection:**

- Antibodies binding to Ga and/or Gb protein (ELISA)

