**4.3.3. Handling of Missing and/or Unquantifiable Immune Response Data**

Missing immune response data will not be imputed.

Values below the lower limit of quantification (LLOQ) will be imputed based on the type of analysis. For the calculation of the geometric mean titer or medians, values below LLOQ will be imputed to LLOQ/2. While for the calculation of the geometric mean increases, values below LLOQ will be imputed to LLOQ.

For G- Elisa ARI Day 3-5 will be treated similar to a baseline and imputation for actual values and fold rise will follow the above.

For ICS assays: the LLOQ will be used if available and validated. In case no validated LLOQ is available then a provisional cut-off will be provided before DBL (only for total cytokine response). For the individual cytokine combinations of IFN $\gamma$ , TNFa and IL2, negative values will be imputed with 0. For descriptive statistics or graphs on actual values, values below the LLOQ will also be imputed to a value of LLOQ/2.

Values above the upper limit of quantification (ULOQ) will be imputed to ULOQ.

The LLOQ and ULOQ values per assay will be available in the database.

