### 5.3. Immunogenicity Analysis

The analysis of immunogenicity will use the PPI set. For both the Immuno subset and the Revaccination Subcohorts, the immunogenicity analysis will follow the analysis outlined in Section 4.3. Except for Revaccination Subcohort B, Post-F ELISA results will no longer be assessed from Day 365 onwards for the Immuno Subset and Revaccination Subcohorts A, C and D.

In addition, for each Revaccination Subcohort separately, geometric mean ratios and corresponding 95% CIs between Day 15 post first vaccination and Day 15 post second vaccination within the group receiving active study vaccine on Day 1 (group 1A, 1B, 1C and 1D respectively) will be calculated for the different assays.

Moreover, the GMT ratios with corresponding 95% CIs of Day 15 post second vaccination for the group receiving active study vaccine twice versus the group receiving placebo first and active study vaccine 1, 2, 3 or 4 years later will also be calculated for the different assays. Therefore, an analysis of variance (ANOVA) model will be fitted with the respective titers as dependent variable and group as independent variable. The point estimate and CIs obtained as such will be back transformed (by exponentiation) to a GMT ratio and the corresponding CI. As a sensitivity analysis, different variances between the groups will be allowed, therefore the CIs will be calculated via Welch's ANOVA.

A similar analysis might be performed at other timepoints as well.

For Revaccination Subcohorts 2A and 2B that get a third vaccination with Ad26.RSV.preF/RSV preF protein mixture or with the individual vaccine components, no formal hypothesis is tested; descriptive statistics over time after the third vaccination will be calculated.

Graphical representations of immunogenicity parameters will be made as applicable.

The impact of baseline factors on the humoral responses will be explored graphically or via descriptive statistics.

Note that tables including descriptive statistics of actual values and fold changes (if applicable) over time might also once be calculated restricted to participants who have data at the last scheduled timepoint included in the respective analyses of the immunosubset and Revaccination Subcohorts. This might also be graphically shown.

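### The immunogenicity set drops samples drawn after natural RSV infection, so the planned G-protein ELISA fold rise cannot be computed on it for RSV-confirmed ARIs

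*SAP*

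**What the plan says.** - **SAP 4.3.2** lists, under its heading for immunogenicity against natural infection, one exploratory assay: "Antibodies binding to Ga and/or Gb protein (ELISA".
- **SAP 2.1.2** gives ARI samples their own windows, counted from ARI onset: relative days 1 to 7 for ARI Day 3-5 and 22 to 36 for ARI Day 29. It adds: "Immunogenicity samples that are not contained in these windows will not be included in the analysis of ARI samples". No population is named for that analysis.
- **SAP 4.3.3** sets the reference sample: "For G- Elisa ARI Day 3-5 will be treated similar to a baseline". The same sentence covers both actual values and fold rise.
- **SAP 4.3** fixes the population: "The analysis of immunogenicity will use the PPI set, focusing on the immunogenicity subset". **SAP 5.3** repeats it for the later seasons and the Revaccination Subcohorts: "The analysis of immunogenicity will use the PPI set".
- **SAP 2.3.2** defines the exclusion. It applies "for participants who experience a natural RSV infection (based on RT-PCR, or other sources" being the grounds given), and its effect is that "samples taken after the natural infection will not be taken into account in the assessment of the immunogenicity". No assay, timepoint or sample type is exempted.
- **SAP 2.3.2** also plans FAS sensitivity analyses that bring the excluded samples back, for key tables and for members of the Immuno Subset or Revaccination Subcohorts.

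**The concern.** Excluding post-infection samples is sensible when the question is what the vaccine induced, because infection raises the same titres. It is the wrong rule for an assay whose purpose is to capture the response to infection. The G-ELISA sits inside the immunogenicity section, so it inherits the PPI and with it the exclusion. The participants whose response the endpoint describes are the ones whose samples are removed.

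What is at stake is whether the G-ELISA table can be produced as intended, and whether it is reproducible. One programmer who applies Section 2.3.2 literally would show fold rises only for ARIs that were not RSV. Another who follows Sections 2.1.2 and 4.3.3 would show RSV-confirmed ARIs as well. Both could cite the SAP.

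**Working it through.** There is no planned figure to reproduce. The check applies the Section 2.3.2 rule to each sample that the G-ELISA uses. I take fold rise to be the ARI Day 29 value divided by the ARI Day 3-5 value, since Section 4.3.3 gives the earlier sample the role of baseline.

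| Sample | Relative day (ARI onset = day 1) | RSV-confirmed ARI, on PPI | RSV-negative ARI with no earlier RSV infection, on PPI |
|---|---|---|---|
| Scheduled samples before the infection | not applicable | kept | kept |
| ARI Day 3-5 | 1 to 7 | dropped if the exclusion runs from onset | kept |
| ARI Day 29 | 22 to 36 | dropped | kept |
| Fold rise (needs both) | | not computable | computable |

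1. **Does the result depend on what counts as after the infection?** Section 2.3.2 does not say whether the clock starts at onset or at the positive test. Suppose ARI Day 3-5 is treated as an acute sample and stays. ARI Day 29 is still at least three weeks after onset and goes. One missing member of the pair is enough to lose the ratio. A reading that started the exclusion only at symptom resolution would rescue just those episodes still running at the Day 29 visit, and the SAP does not state such a reading.

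2. **Is there a written exception?** None appears in Sections 2.3.2, 4.3, 4.3.3 or 5.3. Section 2.1.2 speaks of an analysis of ARI samples but assigns it no population, so Sections 4.3 and 5.3 govern by default.

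3. **Does the FAS analysis replace it?** Only in part. It is a sensitivity analysis, limited to unlisted key tables and to the Immuno Subset and Revaccination Subcohorts. The SAP does not say that the G-ELISA is among the key tables.

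4. **A side effect.** The trigger for exclusion includes sources other than RT-PCR, which are not defined. If serology were one of them, a rise in G-ELISA could itself remove the samples that showed it. The text leaves this open.

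**The case against.** The best counter-argument is that the SAP already handles ARI samples separately. Section 2.1.2 gives them their own window table and their own out-of-window rule, and Section 4.3.3 gives the G-ELISA its own baseline. On that view the specific provisions qualify the general one, and the exclusion was only ever meant for vaccine-response titres. As an account of intent this is probably right. But the qualification is written nowhere, and Section 2.3.2 is unconditional, so the argument shows what the text should say, not what it does say.

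Several stronger readings are tempting and are not supported:

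- **That no samples remain from RSV-confirmed participants.** Their pre-infection samples stay in the PPI, and the later ones return in the FAS sensitivity analyses described above.
- **That the serology-confirmed endpoints of Section 4.4.4.1 lose their RSV-positive group.** Those are exploratory efficacy objectives. Section 4.4.4.3 assigns all such endpoints to the PPE, and Section 2.3.3 has no rule dropping post-infection samples from that set. The search for a fold-rise cut-off is left to the separate CoP SAP.
- **That the Immuno Subset would yield about one case.** With the SAP's 0.75% incidence and 70% efficacy, 100 per arm gives 100 × 0.0075 × (1 + 0.30) = 0.98. That counts Case Definition 2 events, whereas the G-ELISA concerns any RSV infection. It also leaves out the Revaccination Subcohorts, which Table 1 sizes at 2 × (120 + 135 + 120 + 120) = 990 and which Section 2.3.2 names among the five subsets in focus. It is not a usable measure of the loss.

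It also stands that the assay is optional. Section 4.3.2 says only that these responses may be measured, and Section 4.3.4 tests no immunogenicity hypothesis.

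**Conclusion.** The contradiction is real and narrow. On the PPI as defined, the G-ELISA fold rise is unavailable for RSV-confirmed ARIs and available for RSV-negative ones, which is the reverse of what a measure of natural-infection response needs. This is a stated rule that gives the wrong result, not a detail left to another document. It affects one exploratory immunogenicity endpoint and leaves the primary and secondary analyses as they are.

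The conclusion rests on two points: that Sections 4.3 and 5.3 apply the PPI to everything listed in Section 4.3.2, which is their plain wording, and that the fold rise needs the ARI Day 29 sample. I give no expected number of lost results, because the SAP does not state how many ARI samples will be assayed.

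**What to change.** Add to Section 2.3.2, with a cross-reference in Section 4.3 (which Section 5.3 then follows):

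> *The exclusion for natural RSV infection applies to vaccine-response assays at scheduled timepoints. It does not apply to ARI Day 3-5 or ARI Day 29 samples or to G-ELISA results. The analysis of ARI samples includes every participant with an ARI and an available result, whether or not in the Immuno Subset, and is tabulated by RSV RT-PCR status and vaccine group. This does not require assays beyond those already performed.*

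The last sentence matters, because the SAP does not promise that every ARI is assayed. It would also help to state which sources other than RT-PCR count as evidence of infection.

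The cost is an SAP text change and the matching table specification. The ARI windows and the baseline convention are already in place, and no new samples or tests are needed. The vaccine-response analyses at scheduled visits stay as planned.
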